10.4.3 Concentration-QTc analysis

This analysis will be based on the change of QTc from baseline and will use baseline QTc and the concentrations of AQ, DEAQ and relevant analytes/metabolites (when AQ administered alone and in combination with ATV-PG) as covariates. Treatment and time will be used as discrete fixed effects. A series of linear models including one or more of the concentrations will be fitted and the most appropriate one will be selected based on the AIC (Akaike Information Criterion) and the size of the fixed treatment effect. A significant treatment effect (based on an F-test) will be considered an indication for model misfit. For the best fitting linear model, predictions of the effect on QTc will be made at the mean concentrations of the moieties involved at the t_{max} for each of these moieties.

If the per-timepoint analysis described above excludes an effect exceeding 10 ms – i.e. the all confidence intervals are below this value – the best fitting linear model will be accepted. If this is not the case and the best fitting linear model has a significant treatment effect, nonlinear e-max models will also be considered, and predictions will be made based on the best fitting model. In this case, hysteresis between QTc and the concentrations of the relevant analytes and metabolites will be investigated graphically.

Absence of an effect of concern of the IMP on QTc will be concluded if the predictions based on the best-fitting model at the concentrations described above exclude an effect exceeding 10 ms, i.e. the upper limit of the two-sided confidence interval for these predictions is below 10 ms.

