5.4.5 Primary linear model

A series of linear mixed effects model will be fitted. The most comprehensive of these models will be of the form

$$\Delta QTcF \sim C_{ATV} + C_{AQ} + C_{PG} + C_{CG} + C_{DEAQ} + \text{treat} + T + BL$$

where $\Delta QTcF$ is the change from baseline of QTcF, C_{ATV} the plasma concentration of ATV, C_{AQ} the plasma concentration of AQ, C_{PG} the plasma concentration of PG, C_{CG} the plasma concentration of CG, C_{DEAQ} the plasma concentration of DEAQ, treat is a four-level factor with levels placebo, ATV-PG, AQ and ATV-PG + AQ (for placebo, the two monotherapies and the combination therapy respectively) and T is a discrete time effect with one level for each timepoint across study days – i.e. the same time at different days will have different values. This model will allow for treatment and time as categorical fixed effect factors. Concentrations of AQ, DEAQ and relevant analytes/metabolites will be used as covariates.

Note that including a treatment effect will allow some judgement on the appropriateness of the model, as a well-fitting linear model should have a non-significant treatment effect. BL is baseline value for each subject, with the mean across subjects subtracted. No fixed intercept will be allowed.

The model will have random effects per subject for the intercept and the concentration levels. An unstructured covariance matrix will be assumed. If this model does not converge, some or all of the random slopes will be removed, and further simplifications may be performed to reach convergence. Parameter estimation will be using the REML (Restricted Maximum Likelihood) method.

The Kenward-Roger approximation will be used to calculate degrees of freedom and any t-test-based quantities, in particular two-sided 90% confidence intervals for the model parameters.

From the above most comprehensive model, simplified models will be derived by omitting one or more concentration parameters. This will be performed in a stepwise way, by removing the concentration with the smallest absolute t-value from the model. As a result, a series of 5 models with 5 down to 1 concentration will be obtained. For each model, the AIC and the F-value of the treatment effect from an ANOVA will be obtained. If this F-value is significant at the 5 % level, the model will be excluded from the candidate set. For the models remaining, the model with smallest AIC will be chosen as primary.

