Predictions of the effects on QTc of each monotherapy and for the combination therapy will be made at the geometric means of the individual C_{max} values and given together with two-sided 90 % confidence intervals. Predictions will be given for the primary model, and may also be given for other models of interest.

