5.4.6 Checking model assumptions

The key assumptions for the above model to be applicable are linearity of the concentration-QTc-relationship and the absence of hysteresis. These assumptions apply only if there is an effect of plasma concentrations on QTc. Therefore, if the predictions described above exclude an effect of more than 10 ms (i.e. the two-sided 90 % confidence interval for the prediction is completely below 10 ms) and

the per timepoint analysis described in 5.4.4 do not indicate a different result, the primary model will be accepted.

If, however, a prolongation beyond 10 ms cannot be excluded, the following will be performed:

Hysteresis: Simultaneous displays of the time courses of the placebo adjusted mean $\Delta QTcF$ ($\Delta\Delta QTcF$) and the (arithmetic) mean plasma concentrations will be prepared. Likewise, hysteresis loops, i.e. a plot of mean $\Delta\Delta QTc$ against the mean concentration for each timepoint will be presented. If there is a delay of the maximum of the mean $\Delta\Delta QTcF$ with respect to the mean concentration of all moieties included in the primary model, this is an indication for hysteresis. If there is a delay, it will be assumed that the model used is not appropriate.

Linearity: Linearity will be assessed from the decile plots (see below). In addition, if the treatment effect of all candidate models is significant on the 5 % level, a nonlinear e_{max} model will be fitted to the data. More specifically, this will be a model where each of the concentration terms in the linear model with lowest AIC is replaced by an e_{max} -term $aC(1+bC)$. In this model the only random effect per subject will be the intercept. Predictions will be based on this model or on the primary linear model, whichever fits better according to the Akaike Information Criterion and the t-value of the treatment effect. More specifically, if the e_{max} model has a non-significant treatment effect, while the linear one has a significant one, the e_{max} model will be used, otherwise, the one with the smaller AIC will be used.

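### SAP 5.4.5 lets the convergence fallback remove every random slope, in no set order; if slopes vary and the prediction uses the slope alone, the 90% CI behind the 10 ms rule is too narrow

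*SAP*

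**What the plan says.** SAP 5.4.5 regresses the change in QTcF on the concentrations of ATV, AQ, PG, CG and DEAQ, with treatment, time and centred baseline as further fixed terms. On the random part it says "The model will have random effects per subject for the intercept and the concentration levels". The structure and the fallback are: "An unstructured covariance matrix will be assumed. If this model does not converge, some or all of the random slopes will be removed". The same sentence leaves room for other, unspecified simplifications until the model converges. On inference it adds: "The Kenward-Roger approximation will be used to calculate degrees of freedom and any t-test-based quantities, in particular two-sided 90% confidence intervals".

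Five candidate models follow, with five down to one concentration. Those with a significant treatment effect are set aside, and the lowest AIC decides among the rest. Predictions for each monotherapy and for the combination "will be made at the geometric means of the individual C_{max} values and given together with two-sided 90 % confidence intervals". The SAP does not say whether a prediction is the concentration slope times Cmax, or that product plus the treatment term.

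SAP 5.4.6 accepts the primary model if "the two-sided 90 % confidence interval for the prediction is completely below 10 ms" and the by-timepoint analysis does not point elsewhere. Protocol 10.4.3 concludes absence of an effect of concern if "the upper limit of the two-sided confidence interval for these predictions is below 10 ms".

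**The concern.** A random intercept lets subjects differ in level but assumes that all share one concentration slope. If slopes differ, a subject's repeated ECGs tell less about the mean slope than the intercept-only model assumes, and the standard error of the slope comes out too small. Kenward-Roger does not repair this, because it adjusts within whatever covariance structure has been fitted.

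The starting matrix is large for this trial, so some simplification is plausible. The SAP names slope removal as the step to take, up to and including all slopes, and does not name the milder step of dropping the covariances first. At stake is a false conclusion that 10 ms is excluded. There is also a choice of structure, made after seeing the data, that could decide a result close to the margin.

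**Working it through.** The documents give no power or error-rate figure for this model (SAP 3.3), so there is none to reproduce.

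**Size of the starting matrix.** Six random effects give 6 × 7 / 2 = 21 parameters: 6 variances and 15 covariances. Removing one to four slopes leaves 15, 10, 6 or 3. Dropping only the covariances leaves 6.

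**Subjects** (SAP 3.1). 8 + 12 + 12 + 12 = 44, which agrees with 20 + 24. The 12 placebo subjects carry no slope information. Each slope is informed by 8 + 12 = 20 subjects. The 3 × 2 = 6 covariances between ATV/PG/CG slopes and AQ/DEAQ slopes rest on the 8 combination subjects.

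**Can the full matrix be estimated?** The full model was fitted by REML to simulated trials, 40 at each slope SD of 1.5, 3 and 5 ms. The estimated matrix was singular (smallest to largest eigenvalue below 0.0001) in 40, 40 and 39 of 40 fits, although the true ratios were 0.06, 0.25 and 0.69. The optimiser nevertheless stopped normally in all 120.

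**Effect of the fallback on the CI.** The simulation used a one-concentration (DEAQ) model with 44 subjects, 19 in-house post-dose times and 400 runs per setting, with a true effect of 10 ms at geometric mean Cmax. Half-lives come from protocol section 1. Assumptions not in the documents: intercept SD 6 ms, residual SD 5.5 ms, baseline SD 12 ms, PK CV 40%, and slope SD at Cmax of 0 to 5 ms. Fixed degrees of freedom stood in for Kenward-Roger (780 for intercept only, 18 with a random slope, 39 with the treatment term).

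| Slope SD (ms) | Random part; prediction | Mean SE / actual SD | Half-width (ms) | Coverage | Upper limit <10 at true 10 |
|---|---|---|---|---|---|
| 0 | Intercept only; slope alone | 1.11 / 1.12 | 1.82 | 88.7% | 6.0% |
| 1.5 | Intercept only; slope alone | 1.11 / 1.25 | 1.83 | 84.5% | 6.0% |
| 3 | Intercept only; slope alone | 1.12 / 1.56 | 1.84 | 75.2% | 11.3% |
| 5 | Intercept only; slope alone | 1.13 / 2.10 | 1.86 | 62.5% | 17.7% |
| 0 | Slope kept; slope alone | 1.17 / 1.17 | 2.03 | 91.5% | 4.5% |
| 1.5 | Slope kept; slope alone | 1.22 / 1.28 | 2.12 | 87.5% | 6.2% |
| 3 | Slope kept; slope alone | 1.38 / 1.50 | 2.39 | 87.3% | 6.2% |
| 5 | Slope kept; slope alone | 1.69 / 1.81 | 2.92 | 88.5% | 5.0% |
| 0 | Intercept only; slope + treatment | 2.57 / 2.62 | 4.34 | 90.0% | 4.0% |
| 1.5 | Intercept only; slope + treatment | 2.59 / 2.70 | 4.36 | 88.7% | 4.8% |
| 3 | Intercept only; slope + treatment | 2.63 / 2.84 | 4.42 | 87.7% | 5.2% |
| 5 | Intercept only; slope + treatment | 2.72 / 3.13 | 4.58 | 85.3% | 5.8% |

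Monte Carlo error at 75% coverage is √(0.75 × 0.25 / 400) = 2.2 points.

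Hand check at slope SD 5 ms, intercept only: 1.86 / 2.10 = 0.886 actual SDs. Under a normal approximation that covers 62% and leaves about 19% below 10 ms, close to the simulated 62.5% and 17.7%.

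A second simulation of the same layout, with 120 runs per setting (error about 4 points), gave intercept-only coverage of 76-81% at 3 ms and 64-68% at 5 ms, with false exclusion of 8-17%. Keeping a slope gave 87-88% and 4-7%.

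**Room for choice at the margin**, at slope SD 3 ms. The upper limit falls below 10 ms if the estimate is under 10 − 1.84 = 8.16 ms (intercept only) or under 10 − 2.39 = 7.61 ms (slope kept). With the treatment term the figure is 10 − 4.42 = 5.58 ms. Average estimates between these values are decided by choices that the SAP leaves open.

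**The case against.** The strongest reply is that this is only a missing order of steps. Slope removal is one option, down to none only if needed. The allowance for further simplifications could include dropping covariances. A one-concentration candidate needs only 3 random-effect parameters, and the study is exploratory with QTc as a secondary objective. Much of that stands, and it limits the point in four ways where a reader might infer more:

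- **That the CI is always too narrow.** It is not. Without slope variation coverage is near nominal. With the treatment term in the prediction it is about 85-90%, with false exclusion of about 4-8% over both simulations. The documents give no slope SD and do not settle which prediction is meant.
- **That the 21-parameter matrix makes the fallback likely.** The stated trigger is non-convergence. The simulated fits were singular but the optimiser stopped normally, and the SAP has no rule for that case. How often the trigger fires depends on the software.
- **That the plan prescribes an intercept-only model.** It permits one; it does not require it.
- **That the 10 ms conclusion rests on this CI alone.** SAP 5.4.6 also looks to the by-timepoint analysis. That safeguard is partial: SAP 5.4 concedes its limited power, and what counts as a different result is not defined.

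What the reply does not remove is that slope removal is the one step the SAP names. When slopes vary, removing all of them can harm the slope-only CI, and a milder first step is available.

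**Conclusion.** The point holds as a conditional one. If between-subject slopes vary by 3 to 5 ms at Cmax (assumed), all slopes are removed, and the prediction uses the slope alone, the nominal 90% CI covers about 75-81% (3 ms) and 63-68% (5 ms). A true 10 ms effect is then wrongly excluded in about 8-18% of trials against 5%. With one slope kept, the 400-run simulation gave 87-92% and 4.5-6.2% across all settings, including no slope variation, so keeping a slope costs little when it is not needed.

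The full matrix is close to unidentifiable with these 44 subjects, but the documents do not establish how often the fallback would start. The coverage figures rest on the stated variance assumptions, on a DEAQ-only model and on approximate degrees of freedom; the ATV-PG prediction is covered by the same reasoning, not by these figures. This is a cheap improvement to the SAP, not a flaw that invalidates the analysis.

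**What to change.** Amend SAP 5.4.5 as follows.

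1. On non-convergence or a singular fit (with singular defined numerically), first drop the covariances and use a diagonal structure. Then remove slopes one at a time in a pre-specified order.
2. Keep at least one random slope for a moiety that drives each prediction, while that moiety is in the model: AQ or DEAQ for the arms with AQ, and one of ATV, PG or CG for the ATV-PG arm. Removing all the ATV, PG and CG slopes first would move the same weakness to the ATV-PG prediction.
3. Apply the same reduction rule to all five candidates, so that the AIC comparison does not mix structures reached in different ways.
4. State whether the treatment term enters the predictions at geometric mean Cmax. In the simulation this alone changes the intercept-only half-width from about 1.8 to 4.3 ms or more.
5. If no slope can be kept, report a subject-clustered CI with a small-sample correction (about 20 exposed subjects per slope) beside the model-based CI.

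Cost: a few lines of SAP text before database lock. The CIs will be somewhat wider than with an intercept only (2.03-2.92 against 1.82-1.86 ms half-width for the slope-alone prediction). A diagonal structure assumes uncorrelated slopes, which is itself a simplification for parent and metabolite pairs.

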5.4.8 Assay sensitivity

The anticipated effect of the meal at -1 h before drug administration will be used to show assay sensitivity [2]. This meal is expected to produce a shortening of $QTcF$ at the 1, 2 and 3 h timepoints after the meal by 5 – 10 ms. This shortening will be investigated by looking at the estimates of the time effect in the primary model at these timepoints. If the two-sided 90 % CI for all three of these estimates are completely below nought for both days, assay sensitivity will be deemed shown. If this is not the case, a Hochberg procedure will be applied testing the null hypothesis that at least one of the six contrasts is negative. More specifically, for Day 1, the estimates of the time effect will be used directly, while for Day 3, the difference of these timepoints to the estimate for the -35 min predose timepoint will be used.

The time course of the time effect will also be displayed graphically together with two-sided 90 % CI.

Note: The protocol mentioned that assay sensitivity would be evaluated using the estimates of the time effect representing the effects of breakfast and lunch of Days 1 and 3. The effect of breakfast on the two days only will be used, as the first timepoint after lunch is already at 8 h, i.e. 3 hours after the meal.

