5.4.9 PK/J-Tpeak statistical modelling

Similarly to the analysis done for QTc and using the same primary linear model on adjudicated ECGs, an exploratory analysis of J-Tpeak using JTcJ ($J\text{-Tpeak}_c = J\text{-Tpeak}/RR$ power 0.58 with RR in seconds) will be performed to explore the drug related JTcJ interval changes relative to plasma PK concentrations.

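### The primary concentration-QTc model is chosen by AIC across different fixed effects with only REML named; the AIC should come from maximum likelihood fits

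*SAP*

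**What the plan says.** SAP 5.4.5 starts from a mixed model for the change in QTcF with five concentrations (ATV, AQ, PG, CG, DEAQ), treatment, time and centred baseline as fixed effects. Each subject has a random intercept and random concentration slopes. On estimation it says: "Parameter estimation will be using the REML (Restricted Maximum Likelihood) method". The concentration with the smallest absolute t-value is then removed at each step: "As a result, a series of 5 models with 5 down to 1 concentration will be obtained". Models whose treatment F-test is significant at 5% are discarded, and "For the models remaining, the model with smallest AIC will be chosen as primary".

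Neither the SAP nor Protocol 10.4.3, which also selects on AIC, says which likelihood the AIC is computed from. Neither mentions an unrestricted ML fit or fixes the concentration unit.

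SAP 5.4.6 uses AIC again if every candidate has a significant treatment effect. In the e_max model "each of the concentration terms in the linear model with lowest AIC is replaced by" an e_max term. The choice between linear and e_max then goes to e_max if only its treatment effect is non-significant; "otherwise, the one with the smaller AIC will be used".

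**The concern.** The candidates differ in their fixed effects, and that is the setting in which REML likelihoods are not on a common scale. A programmer who follows 5.4.5 literally will read the AIC off the REML fit. The primary model would then depend partly on the unit in which the laboratory reports concentrations.

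Several results hang on that choice:

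- The QTc predictions with 90% intervals come from it: "Predictions will be given for the primary model, and may also be given for other models of interest". Protocol 10.4.3 rests the conclusion of no effect of concern on those predictions excluding 10 ms.
- SAP 5.4.6 accepts the model without examining hysteresis or linearity if the predictions exclude 10 ms and the by-timepoint results agree.
- Assay sensitivity in 5.4.8 reads its time effects from the same model: "This shortening will be investigated by looking at the estimates of the time effect in the primary model at these timepoints".
- The exploratory J-Tpeak analysis in 5.4.9 proceeds "using the same primary linear model on adjudicated ECGs".

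**Working it through.** The plan gives no figure on this point, so there is nothing to reproduce. The check is algebra first, then simulation.

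**Algebra.** With n observations, p fixed effects, covariance V and generalised least squares residual r,

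−2 log L(REML) = (n − p) ln(2π) + ln|V| + ln|X′V⁻¹X| + r′V⁻¹r.

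Multiplying one column of X by c multiplies |X′V⁻¹X| by c², so the criterion moves by 2 ln c. From ng/mL to ug/mL, c = 1/1000 and the move is −2 ln(1000) = −13.816 for each concentration term in the model. ML lacks the ln|X′V⁻¹X| term and does not move. With an unstructured random-slope covariance, the slope variances rescale and V is unchanged, so the result holds for the SAP's default model. The t-values and the treatment F are also unchanged. Units therefore alter neither the removal order nor the F filter, only where along the path selection stops.

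**One simulated data set.** From the documents: 44 subjects (8 on Treatment 1, 12 on each other arm), post-dose times on Days 1, 3 and 4 (17 in all), and half-lives. Assumed: concentration levels, QTc slopes, a random intercept only (SD 6 ms) and residual SD 7 ms. The REML AIC is shown with covariance parameters only in the penalty.

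| Concentrations kept | REML AIC, ng/mL | REML AIC, ug/mL | Difference | ML AIC, either unit |
|---|---|---|---|---|
| 5 | 5132.08 | 5063.00 | 69.08 | 5181.89 |
| 4 (CG dropped) | 5127.00 | 5071.73 | 55.27 | 5180.09 |
| 3 (ATV dropped) | 5111.32 | 5069.88 | 41.44 | 5178.68 |
| 2 (PG dropped) | 5103.61 | 5075.98 | 27.63 | 5178.11 |
| 1 (AQ dropped) | 5105.14 | 5091.32 | 13.82 | 5181.60 |

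The differences are 5, 4, 3, 2 and 1 times 13.816, to rounding. REML picks two concentrations in ng/mL and five in ug/mL; ML picks two in both. Counting all parameters in the penalty, REML picks one in ng/mL (5149.14 against 5149.61 for two) and five in ug/mL. Dropping ATV, the analyte with the largest numerical values, improves the REML AIC by 5127.00 − 5111.32 = 15.68 in ng/mL, by 1.85 in ug/mL, and the ML AIC by 1.41.

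**Frequency of a changed model.** Of 400 such trials, 391 had at least one model passing the F filter. The range covers the two penalty conventions.

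| Comparison | Trials with a different model |
|---|---|
| REML, ng/mL v ug/mL | 376–377 of 391 (96%) |
| ML, ng/mL v ug/mL | 0 of 391 |
| REML in ng/mL v ML | 187–203 of 391 (48–52%) |
| REML in ug/mL v ML | 359–366 of 391 (92–94%) |

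A separate simulation with 19 timepoints and other assumed concentrations gave 18–43% for REML in ng/mL against ML.

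**Frequency of a changed conclusion.** A further simulation used 19 timepoints and 48 settings: eight true DEAQ peak effects from 0 to 15 ms, three concentration levels (Day 3 DEAQ peak 167, 556 or 1668 ng/mL) and two penalty conventions. There were 500 trials per setting, of which 481–495 were usable. It assumed a random intercept of SD 5 ms, residual SD 7 ms, between-subject CV 0.35 and a food effect of −6 ms. The 10 ms verdict is whether the upper 90% limit of the prediction at the geometric mean Cmax is below 10 ms, and a difference in any arm counts.

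| True DEAQ peak effect | Verdict differs, REML ng/mL v ML | Verdict differs, REML ng/mL v ug/mL |
|---|---|---|
| none | 0.6% | 1–2% |
| 3–6 ms | 6–11% | 13–20% |
| 8 ms | 3–5% | 5–7% |
| 10–15 ms | under 1% | under 2% |

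The median change in predicted effect between units was 0.6–0.9 ms. The first step of the assay-sensitivity rule (all six 90% intervals below zero) differed in 1–4% of trials for REML ng/mL against ML.

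**The case against.** The strongest reply is that the SAP never says the AIC is REML-based. The REML sentence concerns parameter estimation, for which REML with Kenward-Roger is suitable, and the AIC sentence names no likelihood. That is true, and if ML was intended the change is only a clarification. But no other method appears in either document, so the literal reading is the wrong one.

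A trial reports in one unit, so the ng/mL against ug/mL frequencies show that the rule is arbitrary rather than how often a result would change. This stands; REML in ng/mL against ML is the practical comparison.

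The simulations use a random intercept only, which is the SAP's fallback. If each slope leaves with its fixed term, the covariance parameters number 22, 16, 11, 7 and 4, so the penalty changes by 12, 10, 8 and 6 AIC units per step, which is of the same order as 13.8. One trial fitted with a random DEAQ slope gave −2 REML log L for 5, 2 and 1 terms of 5711, 5680, 5677 in ng/mL and 5642, 5653, 5663 in ug/mL. Adding penalties of 44, 14 and 8 gives 5755, 5694, 5685 and 5686, 5667, 5671. This is rough, because any likelihood gain from extra slopes is ignored. The contrast shrinks from one term against five to one against two, but the choice still depends on the unit.

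The simulated verdicts also leave out the by-timepoint cross-check in 5.4.6 and the Hochberg step in 5.4.8. For the linear against e_max comparison, no estimation method is given for the nonlinear model, so whether REML is meant there is open. The endpoint is secondary and the study exploratory. All of this limits the consequences without repairing the rule. The by-timepoint analysis is only a partial safeguard, since SAP 5.4 itself grants it limited power to show the absence of an effect.

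**Conclusion.** The concern holds. Read as written, SAP 5.4.5 ranks models on a criterion that is not comparable between them. The shift of 13.8 AIC units per concentration term for a thousandfold change of unit is exact and needs no assumption about the trial.

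The frequencies are illustrative and rest on assumed concentrations, variances and an intercept-only random structure. Within them the identity of the primary model is strongly affected: even with ng/mL fixed, REML and ML disagree in 18 to 52% of trials across the two sets of assumptions. The 10 ms verdict is affected mainly when the true effect is small but not zero, and rarely when it is 10 ms or more. The point should be fixed. It does not undermine the trial's primary safety objective.

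**What to change.** In SAP 5.4.5, add:

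> Candidate models will be compared by AIC from maximum likelihood (ML) fits, with fixed effects and covariance parameters counted in the penalty. The selected model will be refitted by REML with Kenward-Roger degrees of freedom for estimates, confidence intervals and predictions.

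In SAP 5.4.6, state that ML-based AIC is used both to select the concentration terms for the e_max model and to decide between the linear and e_max models.

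It would also help to say whether a removed concentration's random slope is removed with it. Holding one random-effects structure across candidates is optional, because ML AIC with all parameters counted can compare models whose random effects differ.

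The cost is two SAP sentences and one extra ML fit per candidate. Data, design and the method of final inference stay as they are.
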